11.4.3 Serious Adverse Events requiring expedited reporting to the Trial Office

All SAEs not listed in section 11.4.1 or section 11.4.2 must be reported to the Trial Office on a trial specific SAE CRF within 24 hours of the site research team becoming aware of the event.

11.5 SAE Reporting process

On becoming aware that a participant has experienced an SAE which requires expedited reporting on an SAE CRF, the PI or delegate should report the SAE to their own Trust in accordance with local practice and to the Trial Office.

To report an SAE to the Trial Office, the PI or delegate must complete, date and sign the trial specific CRF. The completed form together with any other relevant, appropriately anonymised, data should be submitted to the Trial Office using the information below within 24 hours.

To report an SAE, submit via the trial database

Where an SAE CRF has been completed by someone other than the PI initially, the SAE CRF form will be signed off by the PI to confirm agreement with the causality and severity assessments.

On receipt of an SAE CRF, the Trial Office will allocate each SAE a unique reference number and notify the site via email to the site as proof of receipt. The site and the Trial Office should ensure that the SAE reference number is quoted on all correspondence and follow-up reports regarding the SAE and filed with the SAE in the ISF.

If the site has not received confirmation of receipt of the SAE or if the SAE has not been assigned a unique SAE identification number within 1 working day of reporting, the site should contact the Trial Office.

11.5.1 Assessment of causality of an SAE

When completing the SAE CRF, the PI (or, throughout this section, a medically qualified delegate) will be asked to define the nature of the seriousness and causality (Table 5: Categories of causality) of the event.

In defining the causality, the PI must consider if any concomitant events or medications may have contributed to the event and, where this is so, these events or medications should be reported on the SAE CRF. It is not necessary to report concomitant events or medications which did not contribute to the event.

As per Table 5: Categories of causality, all events considered to be 'possibly', 'probably', or 'definitely' related to the intervention will be reported by the trial office as 'related'; all events considered at site to be 'unlikely' or 'unrelated' to the intervention will be reported by the trials office as 'unrelated'. The same categorisation should be used when describing AEs and protocol-exempt SAEs in the source data.

Table 5: Categories of causality

Category	Definition	Causality
Definitely	There is clear evidence to suggest a causal relationship, and other possible contributing factors can be ruled out.	Related
Probably	There is evidence to suggest a causal relationship, and the influence of other factors is unlikely.	
Possibly	There is some evidence to suggest a causal relationship. However, the influence of other factors may have contributed to the event (e.g., the participant’s clinical condition, other concomitant events or medication)	
Unlikely	There is little evidence to suggest there is a causal relationship. There is another reasonable explanation for the event (e.g., the participant’s clinical condition, other concomitant events or medication).	Unrelated
Not related	There is no evidence of any causal relationship.	

11.5.2 Assessment of expectedness of an SAE by the CI

On receipt of an SAE CRF, the Trial Office will forward it, with the unique reference number, to the Chief Investigator (CI) or delegate(s) who will independently* review the causality of the SAE. An SAE judged by the PI or CI or delegate(s) to have a reasonable causal relationship (“Related” as per Table 5: Categories of causality) with the intervention will be regarded as a related SAE (i.e., SAR). The severity and causality assessment given by the PI will not be downgraded by the CI or delegate(s). If the CI or delegate(s) disagrees with the PI’s causality assessment, the opinion of both parties will be documented, and where the event requires further reporting, the opinion will be provided with the report.

*Where the CI is also the reporting PI an independent clinical causality review will be performed.

The CI or delegate(s) will also assess all related SAEs for expectedness with reference to the criteria in table 6.

Table 6: Categories of expectedness

Category	Definition
Expected	An adverse event that is consistent with known information about the trial related procedures or that is clearly defined in the reference safety information (RSI).
Unexpected	An adverse event that is not consistent with known information about the trial related procedures and/or is not clearly defined in the RSI.

The most recently published Summary of Product Characteristics (SmPC) found on the Electronic Medicines Compendium (emc) for 25mg Transdermal Patches with reference to *Section 4.8 Undesirable effects* will be used for the purposes of the RSI. This is reflective of all NRTs. E-Cigarettes are a commercial product not a medical product. As such there is no requirement for safety profiling and no SmPC to inform the RSI. The most recently published SmPC for 15mg Inhalator will be used as a guide on which to base assessment of expectedness (as per MHRA guidance ref: [Guidance for licensing electronic cigarettes and other inhaled nicotine-containing products as medicines - GOV.UK \(www.gov.uk\)](https://www.gov.uk/guidance/guidance-for-licensing-electronic-cigarettes-and-other-inhaled-nicotine-containing-products-as-medicines)).

The CI will undertake review of all SAEs and may request further information from the clinical team at site for any given event(s) to assist in this.

If the event is unexpected (i.e., it is not defined in the approved version of the RSI) it will be classified as a Suspected Unexpected Serious Adverse Reaction (SUSAR).

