11. ADVERSE EVENT REPORTING

11.1 Definitions

Table 4: Adverse event reporting definitions

Severity Definitions	Mild	Awareness of signs or symptoms that do not interfere with the participant's usual activity or are transient and resolved without treatment and with no sequelae.
	Moderate	A sign or symptom, which interferes with the participant's usual activity.
	Severe	Incapacity with inability to do work or perform usual activities.
Adverse Event	AE	Any untoward medical occurrence in a participant administered a medicinal product and which does not necessarily have a causal relationship with this intervention. Comment: An AE can therefore be any unfavourable and unintended sign (including abnormal laboratory findings), symptom or disease temporally associated with the use of an investigational medicinal product, whether or not related to the investigational medicinal product.
Adverse Reaction	AR	All untoward and unintended responses to an IMP related to any dose administered. Comment: An AE judged by either the reporting Investigator or Sponsor as having causal relationship to the IMP qualifies as an AR. The expression reasonable causal relationship means to convey in general that there is evidence or argument to suggest a causal relationship.
Serious Adverse Event	SAE	Any untoward medical occurrence or effect that: Results in death Is life-threatening* Requires hospitalisation or prolongation of existing hospitalisation Results in persistent or significant disability or incapacity Is a congenital anomaly/birth defect Or is otherwise considered medically significant by the Investigator**
Serious Adverse Reaction	SAR	An AR which also meets the definition of a SAE.

Unexpected Adverse Reaction	UAR	An AR, the nature or severity of which is not consistent with the applicable product information (e.g., Investigator Brochure for an unapproved IMP or (compendium of) Summary of Product Characteristics (SmPC) for a licensed product). When the outcome of an AR is not consistent with the applicable product information the AR should be considered unexpected.
Suspected Unexpected Serious Adverse Reaction	SUSAR	A SAR that is unexpected i.e., the nature, or severity of the event is not consistent with the applicable product information. A SUSAR should meet the definition of an AR, UAR and SAR.

* The term life-threatening is defined as diseases or conditions where the likelihood of death is high unless the course of the disease is interrupted.

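### The expectedness test in Section 11.5.2 overlaps with itself and omits severity and outcome, so it can class a related SAE differently from Table 4

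*Protocol*

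**What the plan says.** Protocol Section 11.5.2 tells the chief investigator or delegate to "assess all related SAEs for expectedness with reference to the criteria in table 6". Table 6 has two rows:

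- **Expected:** the event is "consistent with known information about the trial related procedures or that is clearly defined in the reference safety information (RSI").
- **Unexpected:** the event is not "consistent with known information about the trial related procedures and/or is" not clearly defined in the RSI.

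The section closes with a further rule: "If the event is unexpected (i.e., it is not defined in the approved version of the RSI) it will be classified as" a SUSAR.

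Section 11.1 (Table 4) defines the same terms differently. A SUSAR is a serious reaction for which "the nature, or severity of the event is not consistent with the applicable product information". The entry for an unexpected reaction adds outcome: "When the outcome of an AR is not consistent with the applicable product information the AR should be considered unexpected". Table 4 also requires a SUSAR to meet the definition of an unexpected reaction.

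On the reference document, Section 11.5.2 names "The most recently published Summary of Product Characteristics (SmPC) found on the Electronic Medicines Compendium (emc") as the source of the RSI, while its closing sentence refers to the approved version.

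Section 11.6 attaches the deadlines: 7 days for a SUSAR that is fatal or life-threatening, 15 days for any other SUSAR, and an annual DSUR covering all serious adverse reactions.

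**The concern.** Expectedness is the only step separating a related SAE reported to the MHRA, the ethics committee and the sponsor's governance team within days from one they first see in an annual report. The step needs one definition that puts each event in exactly one category. The protocol gives three (Table 6, the closing sentence of Section 11.5.2, and Table 4), and they do not agree.

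The disagreement that matters most concerns a reaction whose term is in the RSI but which turns out more severe than described there, or has an outcome, such as death, that is not described there. Table 4 treats it as unexpected. The rules the assessor is actually sent to say nothing about severity or outcome.

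**Working it through.** There is no stated figure to reproduce, so the check is logical. Define three conditions for a related SAE:

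- A: consistent with known information about trial procedures (Table 6)
- B: defined in the RSI (Table 6; closing sentence of Section 11.5.2)
- C: severity and outcome consistent with the product information (Table 4)

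I assume that a reaction's nature is consistent with the product information exactly when B holds, and I read and/or inclusively. The rules are then:

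- Table 6 Expected = A or B
- Table 6 Unexpected = not A, or not B
- Closing sentence: unexpected = not B
- Table 4: unexpected = not B, or not C

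| A | B | C | Table 6 | Closing sentence | Table 4 |
|---|---|---|---|---|---|
| yes | yes | yes | Expected | not SUSAR | not SUSAR |
| yes | yes | no | Expected | not SUSAR | **SUSAR** |
| yes | no | yes | both | SUSAR | SUSAR |
| yes | no | no | both | SUSAR | SUSAR |
| no | yes | yes | both | not SUSAR | not SUSAR |
| no | yes | no | both | not SUSAR | **SUSAR** |
| no | no | yes | Unexpected | SUSAR | SUSAR |
| no | no | no | Unexpected | SUSAR | SUSAR |

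**Step 1, Table 6 alone.** The complement of (A or B) is (not A and not B). With and/or, the Unexpected row is wider than that, and both rows hold whenever exactly one of A and B holds. This is 2 of the 4 combinations of A and B.

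**Step 2, Table 6 against the closing sentence.** The closing sentence uses B only, so it gives one answer in every row. For A without B that answer is SUSAR, although the first row of Table 6 calls the event Expected.

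**Step 3, closing sentence against Table 4.** They differ in 2 of the 8 rows, both with B true and C false. Take a related fatal event whose term is in the RSI, but not with a fatal outcome. On the closing sentence it is not a SUSAR and goes only into the annual DSUR. Under Table 4 it is a SUSAR due in 7 days. If the mismatch is one of severity and the event is neither fatal nor life-threatening, the contrast is 15 days against the annual report.

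**Step 4, sensitivity to the reading of and/or.** If it is read as plain and, the overlap in step 1 disappears. The conflicts in steps 2 and 3 remain, because neither depends on that phrase.

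**The case against.** The strongest reply is that Table 4 governs. Section 11.2 points to it for the adverse event definitions, so the closing sentence of Section 11.5.2 is shorthand and the severity and outcome test is already in the protocol. This has weight, but Section 11.2 does not override the instruction to use Table 6, and Section 11.5.2 does not refer the assessor back to Table 4 for this step.

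It can also be said that a fatal outcome absent from the SmPC is not clearly defined there, so Table 6 catches it. That reading is possible, but the text does not state it, and the closing sentence asks only whether the event is defined.

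Three further points stand and limit the finding:

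- The closing sentence settles the Table 6 overlap for reporting. A reader might infer from the Unexpected row that ordinary listed NRT reactions would be sent as SUSARs. The documents do not support that unless the closing sentence is ignored.
- The combination of A without B is narrow. Only events judged related to the intervention reach this test, so an event due solely to blood sampling or spirometry does not. The 2 of 4 figure counts logical combinations and says nothing about how often they occur.
- The delay affects notification of the regulator, the ethics committee and the governance team, not all oversight. SAEs outside the lists in Sections 11.4.1 and 11.4.2 reach the Trial Office within 24 hours, the chief investigator reviews all SAEs, and the DMC may review any of them.

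**Conclusion.** The wording is inconsistent and should be corrected. Table 6 does not define complementary categories. The closing sentence contradicts it for an unlisted reaction consistent with procedure information. Neither carries the severity and outcome criteria of Table 4. The practical consequence is confined to related SAEs that are in the RSI but whose severity or outcome is not consistent with it: a SUSAR due in 15 days (7 if fatal or life-threatening) under Table 4, but annual reporting only on the closing sentence's wording.

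How many events this affects cannot be derived from the protocol, and it may be few. The 7-day deadline should not be generalised, since it covers only fatal or life-threatening SUSARs. Nor should Table 6 itself be described as testing only whether an event is listed. It has a procedure condition as well, and the RSI-only test is in the closing sentence.

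The two descriptions of the RSI version are a minor drafting point. A reader might infer that they lead to different classifications, but the protocol shows no event for which they would.

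The conclusion on severity and outcome assumes that defined in the RSI is taken at its word, as a test of whether the event appears there.

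**What to change.** Reconcile Table 6 and the closing sentence of Section 11.5.2 with Table 4:

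- **Expected:** nature, severity and outcome are all consistent with the RSI.
- **Unexpected:** at least one of them is not.
- Take the procedure condition out of the SUSAR test. If relation to trial procedures is of interest, record it separately.
- Have the closing sentence refer to the revised Table 6 instead of giving its own definition.
- As a minor point, describe the RSI version in the same words where the SmPC is named and in the closing sentence.

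The cost is one table and two sentences in the next amendment, with the SAE review form changed to match, and possibly a few more expedited reports. No outcome, analysis or sample size is affected.

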11.5.3 Provision of SAE follow-up information

Following reporting of an SAE for a participant, the participant should be followed up until resolution or stabilisation of the event. Follow-up information should be provided using the SAE reference number provided by the Trial Office. Once the SAE has been resolved, all critical follow-up information has been received and the paperwork is complete, a copy of the final version of the completed SAE CRF must be submitted to the Trial Office and, if paper, the original kept in the ISF.

11.6 Reporting SAEs to third parties

The independent Data Monitoring Committee (DMC) may review any SAEs at their meetings.

The Trial Office will report details of all SARs (including SUSARs) to the MHRA, Research Ethics Committee (REC), and UoB Research Governance Team (RGT) annually from the date of the Clinical Trial Authorisation, in the form of a Development Safety Update Report (DSUR).

Additionally, the Trial Office will report a minimal data set of all individual events categorised as a fatal or life threatening SUSAR to the MHRA, REC, and RGT within 7 days of being notified. Follow-up information will be provided within an additional 8 days.

All other events categorised as SUSARs will be reported within 15 days of being notified.

Details of all SUSARs and any other safety issue which arises during the course of the trial will be reported to the PIs. A copy of any such correspondence should be filed in the ISF and Trial Master File (TMF).

SUSARs may be reported to the manufacturer of the Investigational Medicinal Product by the trial office within a reasonable timeframe.

11.7 Urgent Safety Measures

If any urgent safety measures are taken, the Trial Office shall immediately, and in any event no later than 3 days from the date the measures are taken, give written notice to the REC and MHRA of the measures taken and the reason why they have been taken.

11.8 Follow-up of pregnancy outcomes for potential SAEs

All trial participants will be current daily smokers at the start of the trial. Nicotine products have a lower risk to health generally and in pregnancy than that expected with smoking tobacco. NICE guidelines support the use of nicotine replacement products during pregnancy for smoking cessation as it is considered safer than cigarette smoking. Therefore, congenital anomalies or birth defects in the offspring of participants will not be reported as part of this trial.

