1.3.2 Justification for inclusion of pregnant women

The trial will not exclude pregnant women. Smoking in pregnancy is associated with increased risks of miscarriage, stillbirth, prematurity, low birth weight, perinatal morbidity and mortality, neo-natal and sudden infant death⁴⁹ and possibly also adverse infant behavioural outcomes.^{50 51} A trial of nicotine patches^{52 53} indicated that nicotine replacement is safe to use in pregnancy, and NICE guidelines recommend NRT to help women stop smoking during pregnancy and in the first year after childbirth.⁵⁴ A trial comparing EC and NRT during pregnancy showed safety outcomes were similar between the two study arms, apart from low birthweight (<2,500 g), which was less frequent in the e-cigarette arm.⁵⁵ Overall, when the choice is between using nicotine products such as NRT or e-cigarettes or continuing to smoke, the use of NRT or e-cigarettes is a recommended option.

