6.2 Exclusion criteria

1. Unable to perform spirometry to a satisfactory standard (e.g. due to dementia, lack of teeth, lack of coordination or not having a good oral seal)
2. Deemed as unsuitable to participate in the trial (e.g. terminal illness, unable to give informed consent)
3. Unable to participate in behaviour support calls
4. Severe angina or unstable cardiovascular disease (CVD)
5. History of end stage kidney disease
6. History of cirrhosis of the liver
7. Currently taking part in another trial of smoking cessation or COPD treatment/management
8. Contraindications to spirometry within the last 12 weeks – tuberculosis infection, cardiac infarction, retinal detachment, Pneumothorax or surgery on the chest, abdomen, brain, ears or eyes (*invite back and re-assess after 12 weeks*)

This will be undertaken by an appropriate member of site staff, delegated this responsibility on the ECAL Site Signature and Delegation Log. In some circumstances it is appropriate to have someone other than a qualified medical doctor assess eligibility. We have conducted a risk assessment and as the safety profile of the IMP is established as low risk and patients will not be put at any higher risk of side effects from either intervention than standard care, and the inclusion and exclusion criteria are straightforward, it is appropriate that eligibility can be delegated to an appropriately trained member of site staff overseen by a medically qualified doctor. Prior to randomisation, the eligibility of each trial participants will be confirmed by a delegated and suitably trained medically qualified doctor at site; confirmation of eligibility will be documented on the baseline assessment visit CRF prior to randomisation.

Details of all patients screened for trial will be recorded on the ECAL Participant Screening/Enrolment Log which will be kept in the ISF and should be available to be sent to the Trials Office upon request.

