11.4 Serious Adverse Event (SAE) reporting in ECAL trial

All adverse events which meet the definition of serious must be recorded in the participant medical notes, including the causality and severity. The reporting period for SAEs will be from randomisation until 26 weeks after agreed set target quit day/ default target quit day. When an SAE is identified during a scheduled telephone call with a participant, the trial team will notify the research site to investigate.

For all SAEs, the PI or delegate must do one of the following:

1. **Record safety reporting-exempt SAEs** in the medical notes but **not report** them to the trials office on an SAE form as per Section 11.4.1 Serious Adverse Events not requiring reporting to the Trial Office.
2. **Report SAEs to the trial office in a non-expedited manner.** This can only be done for the pre-defined subset of SAEs as per Section 11.4.2 Serious Adverse Events requiring non-expedited reporting to the Trial Office.
3. **Report SAEs to the trial office in an expedited manner** (within 24 hours of the site research team becoming aware of the event). All SAEs not covered by the above 2 categories must be reported as per Section 11.4.3 SAE Reporting process.

Note: when an SAE occurs at the same site at which the participant is receiving a trial product or is being followed up for trial purposes, processes must be in place to make the trial team at the site aware of any SAEs, regardless of which department first becomes aware of the event, in an expedited manner.

In addition, any SAE reported to the trial team by the participant will be passed to the PI to ensure the SAE is noted in the participant's medical notes. Where the SAE requires causality assessment, we will follow up with the PI until resolution of the SAE.

11.4.1 *Serious Adverse Events not requiring reporting to the Trial Office*

Safety reporting exempt SAEs must be recorded in the participant medical notes, including the causality and severity, but for trial purposes these events do not require reporting on the SAE CRF. The following will be considered as safety reporting exempt SAEs:

1. Pre-planned elective hospitalisation for any reason
2. Congenital anomalies or birth defects in the offspring of participants

11.4.2 *Serious Adverse Events requiring non-expedited reporting to the Trial Office*

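### The reporting exemption for congenital anomalies has no causality condition, so an anomaly judged related is a serious adverse reaction that the prescribed route cannot bring to the CI, MHRA or REC

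*Protocol*

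**What the plan says.** On enrolment, Protocol section 1.3.2 says "The trial will not exclude pregnant women", and none of the eight exclusion criteria in section 6.2 concerns pregnancy.

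On definitions, Table 4 (section 11.1) includes among the criteria for an SAE that the event "Is a congenital anomaly/birth defect". It carves nothing out of the serious adverse reaction or SUSAR definitions: "A SUSAR should meet the definition of an AR, UAR and SAR".

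On reporting, section 11.4 sorts SAEs into exempt, non-expedited and expedited. Section 11.4.1 lists two exempt kinds: planned elective admissions and "Congenital anomalies or birth defects in the offspring of participants". Exempt events go into the participant's medical notes with causality and severity, "but for trial purposes these events do not require reporting on the SAE CRF". Section 11.8 goes further: "congenital anomalies or birth defects in the offspring of participants will not be reported as part of this trial". Its reason is that nicotine products carry less risk than smoking, in pregnancy as elsewhere.

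On review and onward reporting, section 11.5.2 has the Trial Office forward each SAE form to the Chief Investigator on receipt. It treats any SAE judged related by either the site or the Chief Investigator as a serious adverse reaction, and says the Chief Investigator reviews all SAEs. Section 11.6 adds: "The Trial Office will report details of all SARs (including SUSARs) to the MHRA", together with the ethics committee and the sponsor's governance team.

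**The concern.** The exemption is defined by type of event alone. Planned elective admission, the other exempt item, is fixed in advance and is unlikely to be a reaction to a trial product. A congenital anomaly could be one. The protocol asks the site to judge whether it is, and then gives that judgement nowhere to go.

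What is at stake is safety oversight. If a related and unexpected anomaly occurred, following the protocol to the letter would mean no expectedness assessment, no SUSAR classification, no 7- or 15-day report and no entry in the annual safety report. The trial would then be in breach of its own section 11.6 while complying with 11.4.1 and 11.8. The reason given in 11.8 supports letting pregnant smokers take part. It does not explain why an event already judged related should be held back from review.

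**Working it through.** The protocol gives no figure for this point, so the check is to trace one event through the sections. Take a participant who enrols while pregnant and whose child is found to have an anomaly inside the SAE window.

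1. **Is it an SAE?** Yes. Table 4 lists it, and 11.4.1 itself classes it among the exempt SAEs.
2. **Is causality judged?** Yes. Section 11.4.1 requires causality in the notes, and 11.5.1 says the Table 5 categories also apply to exempt SAEs in the source data. The site may therefore write possibly, probably or definitely, each of which counts as related.
3. **What does a related grading make it?** A serious adverse reaction, because 11.5.2 accepts the site's judgement alone. (Table 4 words a reaction in terms of the IMP, and 8.5.1 says the e-cigarette is not one. However, 11.5.2 speaks of the intervention and names reference documents for both products, so the step is read here as covering both arms.)
4. **Is an SAE form raised?** No. Section 11.4.1 does not require one, and 11.8 says the event is not reported.
5. **Does the Chief Investigator review it?** The only trigger in 11.5.2 is receipt of an SAE form. Without one there is no independent causality review, no expectedness assessment and no SUSAR classification.
6. **Does it reach the MHRA and REC?** Section 11.6 promises all serious adverse reactions, but the Trial Office has no form to report from.
7. **Is there another route?** If the participant mentions the event on a call, 11.4 has the trial team pass it to the site's investigator for the notes. That does not lift the exemption.

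Steps 3 and 4 show the conflict. The statements in 11.5.2 and 11.6 have no exception, and 11.4.1 and 11.8 have no causality condition. For a related anomaly they cannot all be followed.

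**Size.** The protocol gives neither a pregnancy rate nor an anomaly risk, so both are assumed.
- Pregnancies: 0 to 0.5% of 1250; 1250 × 0.005 = 6.25, so 0 to about 6.
- Anomaly risk per pregnancy: 2% to 5%.
- Expected anomalies with 6 pregnancies: 6 × 0.02 = 0.12 to 6 × 0.05 = 0.30. With none, 0.
- Chance of at least one with 6 pregnancies: 1 − 0.98^6 = 0.11 to 1 − 0.95^6 = 0.26.

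The number judged related would be smaller again.

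**Window.** SAE reporting runs from randomisation to 26 weeks after the target quit date (11.4), which is set about 2 weeks after baseline (8.1.1): 2 + 26 = 28 weeks. Taking term as 40 weeks, a participant at least 40 − 28 = 12 weeks pregnant at baseline would reach term inside the window. A pregnancy conceived after randomisation would not.

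**The case against.** The strongest defence is that the exemption is deliberate, stated the same way in two places and reasoned. Table 4 gives general definitions and 11.4 then sorts SAEs by how they are reported, so listing a kind of SAE as exempt does not in itself contradict Table 4. That is right, and the point does not rest on Table 4 against 11.4.1. It rests on 11.5.2 and 11.6, which speak of all SAEs and all serious adverse reactions without qualification.

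A reader might also infer more than the text supports:

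- *That all fetal harm goes unreported.* It does not. Only anomalies and birth defects are exempt. Other pregnancy events named in 1.3.2, such as miscarriage or stillbirth, fall under the 24-hour rule of 11.4.3 whenever they meet a Table 4 criterion.
- *That an anomaly could never come to light.* It is still written in the notes with causality and severity, trial staff may see source documents (13.2.1), 11.4 mentions following up with the investigator where causality assessment is required, and the DMC may review any SAEs (11.6). The gap is in the prescribed route to formal review.
- *That the exemption causes a total loss of such reports.* Many births would fall outside the SAE window whatever the exemption said.
- *That the protocol ignores the comparison between the two products in pregnancy.* Section 1.3.2 cites a trial of e-cigarettes against NRT in pregnancy with similar safety outcomes, apart from low birthweight, which was less frequent with e-cigarettes. That supports inclusion. It does not address a related event in this trial.

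The objection that numbers are tiny stands in full. It limits the importance of the point but does not remove the conflict.

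**Conclusion.** The concern holds in a narrow form. For a congenital anomaly judged related, sections 11.4.1 and 11.8 cannot be followed together with 11.5.2 and 11.6. This is a conflict between stated safety rules, not detail left for a later document.

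The likeliest number of affected events is zero on the assumed rates, which are illustrative and not taken from the protocol. The primary outcome, the sample size and every efficacy analysis are unaffected. The point is worth correcting because the event would be rare but serious, the protocol chooses to admit pregnant women, and the correction is cheap. It does not show that fetal safety in general is unmonitored.

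**What to change.** Reconcile sections 11.4.1 and 11.8 with 11.5.2 and 11.6. There are two ways:

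- remove item 2 from 11.4.1 and the closing sentence of 11.8, so that anomalies are handled like any other SAE; or
- at minimum, limit the exemption to events judged unrelated, so that any anomaly graded possibly, probably or definitely related goes on an SAE form for Chief Investigator review. If this option is taken, 11.5.2 should also say that its review of all SAEs leaves out those that remain exempt.

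Either way, state how the rule applies to an anomaly found after the SAE window closes at 26 weeks from the target quit date. Otherwise the change would reach only pregnancies already under way or anomalies detected early.

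The cost is a short protocol amendment and at most a few forms. Active follow-up of pregnancy outcomes is not part of this fix. It would be a separate addition, and the consent described in section 7.3 covers telling the GP about participation, not clearly the retrieval of outcomes.
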